Additional preliminary data is needed to support the conduct of a large randomized non-inferiority trial to compare our Facebook-delivered post-partum weight loss intervention to in-person delivery of the intervention. In our pilot study, some intervention posts garnered low or no participant engagement. We have identified posts with low and high participant engagement, and will solicit feedback from women on how to make low engagement posts more engaging. As noted in the grant proposal (Section 3.B/Impact), the research described in this protocol is a step in a line of investigation to develop and test the efficacy and effectiveness of a Facebook-delivered post-partum weight loss intervention. Subsequent steps of this program of research include implementation in real-world settings. It is possible that the best model for widespread dissemination would be to develop a commercial product.

This project has three Specific Aims:

Aim 1: Feasibility. We will examine the feasibility of recruitment (especially the proportion of women unwilling to be randomized to either condition), sustained participation, contamination, retention, and

feasibility of assessment procedures, particularly measurement of cost-related data, in both treatment conditions. We will describe weight loss as an exploratory outcome.

Aim 2: Intervention refinement. In post-intervention focus groups, we will solicit women's feedback on posts with low engagement, and will iteratively refine these posts to make them more engaging.

Aim 3: Measuring time on Facebook. We will compare self-reported time spent on Facebook to participate in the intervention with application-tracked time on Facebook, changes in use, and time spent visibly engaging, to develop procedures for measuring time that balance accuracy and participant burden.

Please see the Specific Aims (page 1) and sections 3.A through 3.D.1.5 of the enclosed grant application (pages 2-7) for additional background information supporting the proposed research. The current protocol will cover research activities described as Phase 2 in the grant application; a separate protocol covers research activities described as Phase 1 (IRB # H17-203).

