Baseline assessment. Staff will call and/or email participants within 3 days of their scheduled baseline assessment to remind them of the appointment. The baseline assessment will include informed consent measurement of height and weight, completion of a contact information sheet, and completion of additional measures which will be used to determine eligibility (screeners for depression and binge eating disorder). Study personnel will also help participants download My Fitness Pal app (all) and an app to track time on Facebook (Android users) and provide instruction of how to use these apps. For iPhone users, personnel will also show them how to locate Facebook app usage data using the battery settings. We expect the baseline study visit to take 30-45 minutes. Following the baseline assessment, research staff will fax the medical clearance form to participants' primary care provider or OBGYN. After the baseline visit, staff will email participants a link to complete a survey via REDCap. A copy of the baseline survey is enclosed. We will email participants a \$20 gift card after they have completed the baseline visit and online survey.

Orientation Webinar. Participants will complete a 60-minute orientation webinar. The purpose of the webinar is to educate participants about what research is, review study procedures, review importance of participation of enrolled participants, and to allow participants another opportunity to evaluate if joining this study is the right choice for them. This webinar is being conducted to improve study retention. The webinar moderator will record in REDCap tracking which participants completed the webinar.

Pre-Randomization Survey. Following the orientation webinar, we will email participants a short online survey that includes Facebook time measures and completion of a randomization agreement. We will email participants a copy of the randomization agreement form for their records. A copy of the pre-randomization survey is enclosed.

Participants will need to complete the telephone screening, baseline assessments (visit and survey), and orientation webinar, and pre-randomization survey before being randomized.

Randomization. We will randomize participants 1:1 to the FB and IP conditions in randomly permuted blocks of size 4 and 6. Randomization will be stratified by weeks post-partum at enrollment (8 weeks to <6 months, 6-12 months) and smartphone type (iPhone vs Android) .

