Weight loss intervention. The 6-month intervention will include dietary and exercise counseling and tips to help participants meet their healthy lifestyle goals. Participants will receive personalized calorie and physical activity goals to help them achieve a healthy weight loss of 1-2 pounds per week. Breastfeeding women will receive daily calorie goals that will facilitate weight loss while accounting for energy needs to support lactation; weight loss expectations do not differ by breastfeeding status. Participants will be encouraged to increase physical activity to 150 minutes per week of moderate intensity activity. While we will provide information about specific exercises designed to help with recovery from childbirth (e.g., pelvic floor exercises), participants will not be required to engage in any particular exercises or activity program. Counselors will encourage and support participants to make a plan for incorporating regular physical activity into their lives in a way (i.e., duration per session, frequency per week) that works for that individual woman. We will encourage participants to track their diet and exercise daily. We will encourage participants to use My Fitness Pal to track their diet and activity. In the in-person condition, the intervention will be delivered via weekly 90-minute group meetings for the first four months and then every other week in months 5 and 6. In the Facebook condition, the intervention will be delivered via a secret (private) Facebook group. See section 3.D.2.2.9 (3.D.2.2.9.1 through 3.2.2.9.6; pages 9-10) of the enclosed grant application for more details on the interventions.

Due to weather or to prevent spread of illness (e.g., coronavirus), we may hold intervention meetings for the in-person condition via video or telephone conference call.

Weekly time survey. Weekly, participants in both treatment conditions will complete a brief online survey to report current weight and time spent on Facebook. We expect the survey to take less than 5 minutes. The survey will be administered via REDCap. A copy of the weekly survey is enclosed.

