Aim 3: Measuring time on Facebook. We will compare self-reported time spent on Facebook to participate in the intervention with application-tracked time on Facebook, changes in use, and time spent visibly engaging, to develop procedures for measuring time that balance accuracy and participant burden. We will compare self-reported time spent on Facebook to participate in the intervention with (1) application-tracked time spent on Facebook, (2) change in application-tracked time over the intervention, and (3) estimated time spent visibly engaging in the intervention using paired t-tests and Wilcoxon rank-sum tests, as appropriate. We will also examine accuracy in reporting total time on Facebook at baseline and adjust self-reported time spent on Facebook to participate in the intervention accordingly. From these comparisons, we will develop procedures for measuring time spent on Facebook to participate in the intervention that maximize accuracy while not placing undue burden on participants nor changing their behavior as a result of surveilling their social media activities.

Inclusion/Exclusion Criteria: [List ALL inclusion and exclusion criteria. Any proposed exclusion criterion based on gender (women of childbearing potential), age, or race must include justification for the exclusion. Describe the conditions under which participants may be removed from the study, i.e., noncompliance with study rules, study termination, etc.]

Only women will be included as the aim of this study is to refine a post-partum weight loss intervention.

Inclusion criteria. Women aged ≥ 18 years, 8 weeks to 12 months post-partum at enrollment, overweight or obese ($BMI \geq 25$ kg/m²) per measured height and weight at the baseline visit, owns a scale (we will provide women with a scale if needed), comfortable reading and speaking English, owns an iPhone or Android smartphone, active Facebook user as defined as daily Facebook use and posts/comments at least weekly over the past 4 weeks, clearance from primary care provider or obstetrician/gynecologist, willing and able to participate in either treatment condition (Facebook or in-person), available to attend in-person meetings over the 6-month study period in Hartford, CT, 45 minutes or less to travel to intervention meetings, and willing and able to provide informed consent.

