Feasibility of assessment procedures. We will examine the extent and mechanisms of missing data, particularly measures of costs associated with delivering and receiving the intervention. For measures with an unacceptable amount of missingness, we will consider alternate measures in the subsequent non-inferiority trial. We will resolve any issues arising in the collection of data needed for the cost-effectiveness aim of the subsequent efficacy trial and develop procedures for assessing time spent on Facebook to participate in the intervention.

Weight loss (exploratory)

We will report percent weight loss at 6 months and 12 months in each treatment condition.

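### Aim 3 names the Wilcoxon rank-sum test, an independent-samples test, for comparing two time measures taken on the same woman; the paired test is the signed-rank test

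*Protocol*

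**What the plan says.** The Aim 3 paragraph of the protocol's Data Analysis section sets one measure against three others: "We will compare self-reported time spent on Facebook to participate in the intervention with (1) application-tracked time spent on Facebook", then the change in tracked time during the intervention, and third "estimated time spent visibly engaging in the intervention using paired t-tests and Wilcoxon rank-sum tests, as appropriate". The Specific Aims give the same comparison without naming a test.

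The data sources are described under the study procedures. In the Weekly time survey paragraph, "participants in both treatment conditions will complete a brief online survey to report current weight and time spent on Facebook". Tracked time comes from the participant's own phone: the Baseline assessment paragraph has staff help women install "an app to track time on Facebook (Android users) and provide instruction of how to use these apps", while iPhone users are shown where their phone's battery settings display Facebook use.

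The SAP names no test for this aim. Under Feasibility of assessment procedures it says only that the team will "develop procedures for assessing time spent on Facebook to participate in the intervention".

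**The concern.** Every Aim 3 comparison puts two numbers from the same woman side by side, so the unit of analysis is the pair. The paired t-test respects this. The rank-sum test does not: it pools the two columns, ranks all the values, and uses a null variance that assumes no relation between the columns. The non-parametric counterpart of the paired t-test is the Wilcoxon signed-rank test.

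Women who report more time will plausibly also have more tracked or visible time. If so, the rank-sum variance is too large, its p-values are too large, and a modest gap between self-report and the comparator is more easily missed. That matters for this aim because the comparisons are meant to settle how time will be measured in the later trial, balancing accuracy against burden. A test that rejects too rarely makes it easier to read a non-significant result as evidence that low-burden self-report is accurate enough.

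**Working it through.** **No figure to reproduce.** The documents give no sample size, alpha, power or correlation for Aim 3.

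**Inputs from the documents**
- Pairs: at most 36 if the Facebook condition is analysed (Justification of Sample Size, 36 per condition).
- Pairs at the retention the protocol calls acceptable: 0.80 × 36 = 28.8, so about 29.

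**Assumptions, not in the documents**
- Minutes log-normal, with log SD 1 for both measures.
- Correlation on the log scale (ρ) of 0, 0.3, 0.5 or 0.7.
- A true shift of 0, 0.4 or 1 log SD.
- Two-sided alpha 0.05.

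**Step 1: type I error by formula.** With equal marginal distributions and no shift, the large-sample variance of the rank-sum statistic on paired data is (1 − ρ_S) times the variance the test assumes, where ρ_S = (6/π)·arcsin(ρ/2) is the rank correlation. The actual error rate is therefore about 2·[1 − Φ(1.96/√(1 − ρ_S))].

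| ρ | ρ_S | 1.96/√(1 − ρ_S) | Actual type I error |
|---|---|---|---|
| 0 | 0 | 1.96 | 5.0% |
| 0.3 | 0.288 | 2.32 | 2.0% |
| 0.5 | 0.483 | 2.73 | 0.6% |
| 0.7 | 0.683 | 3.48 | 0.05% |

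**Step 2: simulation at the trial's size.** 10,000 replicates per cell, both tests run on the same pairs in raw minutes.

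| | ρ = 0 | 0.3 | 0.5 | 0.7 |
|---|---|---|---|---|
| Type I error, 36 pairs, rank-sum | 5.1% | 2.3% | 0.7% | 0.15% |
| Power, 0.4 SD shift, 36 pairs, rank-sum | 37% | 35% | 33% | 29% |
| Power, 0.4 SD shift, 36 pairs, signed-rank | 34% | 43% | 56% | 76% |
| Power, 0.4 SD shift, 29 pairs, rank-sum | 30% | 28% | 24% | 20% |
| Power, 0.4 SD shift, 29 pairs, signed-rank | 26% | 36% | 46% | 66% |

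Signed-rank type I error stays near 5% in all these settings. The simulated rank-sum error rates agree with the formula to within simulation and small-sample error.

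**Step 3: where the choice hardly matters.** For a 1 SD shift both tests have at least 96% power with 36 pairs and at least 92% with 29. At ρ = 0 the rank-sum test is valid and loses nothing. With negative correlation the error reverses: at ρ = −0.3 and 36 pairs, rank-sum type I error is 8.0%.

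**Step 4: limits of the replacement test.** The signed-rank test assumes the within-woman differences are symmetric about their median under the null. With unequal spreads (log SDs of 1 and 0.5, also assumed), equal medians and 36 pairs, it rejects on raw minutes about 10% of the time at ρ = 0, rising to about 16% at ρ = 0.7. Moving to signed-rank repairs the pairing but does not remove the need to look at the shape of the differences.

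**The case against.** The best case against giving this much weight has five parts.

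- **It is probably a naming slip.** The same phrase names the paired t-test, so the authors know the data are paired, and a competent analyst would probably run signed-rank. This may be so. But the text lets the analyst choose only between the two named tests, and nothing in Aim 3 compares independent groups, so an analyst following it literally would run the wrong procedure.
- **The harm may be small in each comparison.** Total tracked time is wider than participation time and visible engagement is narrower, so those differences may be large and found by either test. Change in tracked time may correlate weakly with self-report. This stands and limits the size of the point.
- **Little rests on a p-value.** The SAP reports feasibility outcomes descriptively, and its only text on Facebook time sits among them. The protocol sets no decision rule for Aim 3 and also plans a baseline check of reporting accuracy. This stands too, although the SAP does not withdraw the protocol's tests.
- **The simulation does not fit every comparison.** A change in tracked time can be zero or negative, so the log-normal figures do not apply to the second comparison. Equal spreads are also an assumption. Both criticisms are right; the figures show direction and scale and do not predict the result.
- **The weekly survey text does not mention participation time.** It says time on Facebook, and the form itself is not in these documents, so which item captures participation time is an inference. The pairing does not depend on it.

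**Conclusion.** The concern holds. All three comparisons are within-woman, the only non-parametric test named is for independent samples, and the SAP does not correct it. The consequence depends on positive within-woman correlation, which the documents do not give. Under the stated log-normal assumptions with 36 pairs and a 0.4 SD shift, the rank-sum test gives up about 8 percentage points of power at correlation 0.3 (35% against 43%), 23 at 0.5 (33% against 56%) and 47 at 0.7 (29% against 76%). It gives up nothing at zero correlation and almost nothing for a 1 SD shift. These figures do not cover the comparison with change in tracked time. No trial conclusion turns on this test alone, but it is wrong as written and should be corrected.

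**What to change.** In the Aim 3 paragraph of the protocol's Data Analysis section, replace rank-sum with signed-rank. State that the test is applied to within-woman differences, with one difference per woman, so that repeated weekly reports are first reduced to a single value over a stated period. Put the same wording in the SAP, which now has none for this aim.

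For each of the three comparisons, report the mean or median within-woman difference with its 95% confidence interval. A non-significant test does not show that self-report is accurate; an interval shows how large an error remains plausible. Inspect the distribution of the differences. Where it is clearly asymmetric, a sign test, or an analysis of log minutes when both measures are positive, avoids the symmetry problem shown in Step 4.

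The cost is one wording change, a short addition to the SAP, and three estimates with intervals. No new data are needed.

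### Unless the surveys already ask about device, three steps in Aim 3 (the baseline accuracy check, the adjustment built on it, and the comparison with change in tracked time) would count off-phone Facebook use as over-reporting

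*Protocol*

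**What the plan says.** **Who is enrolled.** The Protocol's inclusion criteria require that a woman "owns an iPhone or Android smartphone, active Facebook user as defined as daily Facebook use and posts/comments at least weekly" over the preceding four weeks. Phone ownership and Facebook use are separate conditions. Nothing there, or in the exclusion criteria, says that Facebook must be used on the phone or through its app.

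**What is tracked.** Under Baseline assessment, staff help participants install "an app to track time on Facebook (Android users" only); for iPhone users, "personnel will also show them how to locate Facebook app usage data using the battery settings". No tracking on a computer or tablet is described anywhere. The section on potential harms does refer to Facebook's website as well as its mobile application, so access outside the app is foreseen.

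**What is self-reported.** The pre-randomization survey contains Facebook time measures. Each week, "participants in both treatment conditions will complete a brief online survey to report current weight and time spent on Facebook". These surveys are enclosed with the Protocol but are not part of the public text, so the wording of the items cannot be seen.

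**What is compared.** Under Data Analysis, Aim 3, self-reported intervention time is set against "1) application-tracked time spent on Facebook, (2) change in application-tracked time over the intervention", and, third, an estimate of time spent visibly engaging. The section continues: "We will also examine accuracy in reporting total time on Facebook at baseline", and says that self-reported intervention time will be adjusted in line with the result. The form of the adjustment is not given. The SAP says only that procedures for assessing Facebook time will be developed, in connection with the cost-effectiveness aim of the later trial.

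**The concern.** Phone-tracked time is the only source of total Facebook time, other than self-report, that the documents describe. It is therefore the natural reference for the baseline accuracy check. If a woman's report covers all her Facebook use and the tracker covers only her phone, the check compares all devices with one device. The difference is a coverage gap, but it would be read as reporting error and then carried into her intervention time as a correction. The comparison with change in tracked time has a similar problem, because any participation on another device is missing from the tracked side.

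The error runs one way, since incomplete device coverage can only lower tracked time. Aim 3 exists to choose how participant time on Facebook will be measured in the later trial, where it feeds the cost comparison. A one-directional error at this stage could steer that choice, and averaging over more women would not remove it.

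**Working it through.** The plan states no figure on this point, so there is nothing to reproduce. The check takes a woman who reports her time exactly and asks what each Aim 3 step would show.

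**Inputs**
- General Facebook use: 50 min/day, from the Protocol's background section, or 50 × 7 = 350 min/week. Illustration only.
- Intervention time: 90 min/week, from Design, Procedures, Materials and Methods. Illustration only.
- Share u of Facebook time that the phone tracker misses: not given in the documents. Assumed, and shown at 10%, 25% and 40%.
- General use is taken to stay at 350 min/week during the intervention, so true total time becomes 350 + 90 = 440.

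**Step 1, baseline check (u is the untracked share of total time).** Tracked time = 350(1-u). Apparent over-report = 350u min/week, or u/(1-u) relative to tracked time: 0.10/0.90 = 11%, 0.25/0.75 = 33%, 0.40/0.60 = 67%.

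**Step 2, adjustment.** If it is proportional (an assumption), a correct 90 min becomes 90(1-u).

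**Step 3, change in tracked time (u is the untracked share of intervention time).** Tracked change = 90(1-u). Apparent over-report = 90u min/week, again u/(1-u) in relative terms.

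**Step 4, total tracked time (same u for all use).** Self-reported intervention time minus tracked total = 90 - 440(1-u).

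| u | Baseline tracked (reported 350) | Apparent over-report at baseline | 90 min after adjustment | Apparent over-report against tracked change | Self-report minus total tracked |
|---|---|---|---|---|---|
| 0% | 350 | 0 | 90 | 0 | -350 |
| 10% | 315 | 35 (11%) | 81 | 9 (11%) | -306 |
| 25% | 262.5 | 87.5 (33%) | 67.5 | 22.5 (33%) | -240 |
| 40% | 210 | 140 (67%) | 54 | 36 (67%) | -174 |

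All entries are min/week except u and the percentages in brackets.

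**Reading the last column.** This comparator includes non-intervention use, so the gap is negative to begin with, and untracked use narrows it. The sign turns only when 440(1-u) falls below 90, that is when u exceeds 1 - 90/440 = 0.795, or about 80%.

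**Visible engagement.** This estimate does not come from the phone tracker, so u does not enter.

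**A side effect of steps 2 and 3.** If the same u applies to both and the adjustment is proportional, adjusted self-report and tracked change are both 90(1-u). At u = 25% both give 67.5 min. The two measures would agree while each is 22.5 min short, so their agreement would not show that either is accurate.

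**The case against.** The strongest objection is that the survey items are not visible. The Protocol gives only the topic of the weekly and pre-randomization questions. They may already ask about time in the phone app, or about device. This stands, and the point is conditional on it. Even so, neither the Protocol's analysis section nor the SAP describes an analysis that uses device information.

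Four stronger readings are tempting, and the documents do not support them.

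- A reader might infer that all of Aim 3 is biased towards over-reporting. The bias is confined to the baseline check, its adjustment and the comparison with change in tracked time. The comparison with total tracked time moves differently, and the visible-engagement comparison does not use the tracker.
- A reader might infer that only Facebook app use is captured on every phone. That is explicit for iPhone. The Android tool is unnamed and may or may not record use in the phone's browser. Nothing suggests that it records a computer or tablet.
- A reader might infer that the later trial will understate participant time in its Facebook arm. The Protocol does not commit to tracked time as the chosen measure and gives no adjustment formula. Aim 3 is developmental, and the SAP undertakes to resolve problems in collecting cost data first. The risk is real if the adjustment is applied without allowing for coverage, but it is not a settled consequence.
- A reader might infer that eligibility is too loose. The criteria show why off-phone use can occur, but the gap lies in measurement and analysis.

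**Conclusion.** The point holds in conditional form. As described, tracked time covers the phone only, while neither eligibility nor the visible description of self-report is limited to that phone. If the enclosed surveys do not ask about device or phone-app time, a woman who reports accurately but uses Facebook elsewhere is scored as over-reporting by u/(1-u) in the baseline check, and in the comparison with change in tracked time. The adjustment then turns the baseline discrepancy into a downward correction of intervention time.

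Over an assumed u of 10% to 40% the apparent over-report is 11% to 67%. Here u is the untracked share of total time for the baseline check and of intervention time for the change comparison, and the two shares need not be equal. The documents give no device split, so this range shows sensitivity and does not estimate the actual error. The direction does not depend on u. The adjusted figures also assume a proportional correction, and the change comparison assumes that other Facebook use stays constant.

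The Aim 1 feasibility outcomes other than the measurement of participant time are not touched. This is an inexpensive improvement to Aim 3 and worth making.

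**What to change.** 1. Check the enclosed pre-randomization and weekly surveys. If they do not already ask, add an item on the share of Facebook time spent in the Facebook app on the tracked phone. Ask it for total time in both surveys, and for intervention time in the weekly survey of the Facebook condition.
2. State in Aim 3 and the SAP that the baseline accuracy check, the adjustment and the comparison with change in tracked time use the phone-app portion of self-reported time. Report the untracked share alongside.
3. Do not adjust self-reported intervention time downward as if phone-tracked time were complete.
4. Use restriction to women, or weeks, with nearly all use in the phone app only as a sensitivity analysis.
5. State whether the Android tool captures use in the phone's browser.
6. If data collection is closed (the SAP is dated 10/20/2021), use any device information held and show the adjustment over a range of u.

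Eligibility need not change.

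**Cost.** One or two items in a weekly survey expected to take under 5 minutes, plus a sentence or two of analysis text. The device share is itself self-reported, so recall error enters the correction as well. The restricted analysis would rest on a smaller, selected part of the roughly 36 women planned for the Facebook condition, which is why it should not be the main analysis.
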